6.2.2 FORMULATION, APPEARANCE, PACKAGING, AND LABELING

The study packaging will be performed by PCI Pharma Services. All packaging and labeling operations will be performed according to Good Manufacturing Practice for Medicinal Products and the relevant regulatory requirements.

Details of packaging and labeling are in final study documentation provided by PCI Pharma Services.

6.2.3 PRODUCT STORAGE AND STABILITY

The study medication must be stored in a secure area at site, accessible only to the investigator and his/her designees. The study medication will be administered only to patients entered into the clinical study, in accordance with the conditions specified in this protocol.

The study medication is to only be prescribed by the principal investigator or his/her named sub-

investigator(s) or a pharmacist, and is to only be used in accordance with this protocol. The study medication must only be distributed to patients properly qualified under this protocol to receive study medication.

The investigator must keep an accurate account of the study medication received from the supplier. This includes the amount of study medication dispensed to patients, amount of study medication returned to the investigator by the patients, and the amount returned or disposed upon the completion of the study. A detailed inventory must be completed for the study medication.

All study medication will be returned to the sponsor or their designee or destroyed at the study site, following end of study and drug reconciliation by the site CRA. The return or disposal of study medication will be specified in writing. AZR-MD-001 is to be refrigerated between 2 – 8°C until opened and protected from light. Maintenance of a temperature log (manual or automated) is required at the clinical sites.

6.2.4 PREPARATION

Patients should let the study tube equilibrate at room temperature below 25°C for up to 15 minutes before dosing. Patients will use the study medication directly from the dose container in accordance with the protocol and should return the dose container to refrigeration between 2 – 8°C following successful dosing. For the next day of dosing, this process should be repeated. This in use pattern should continue for 30 days at which time the dose container should be used for a final day of dosing and then discarded.

6.3 MEASURES TO MINIMIZE BIAS: RANDOMIZATION AND BLINDING

During the Cohort 1 run-in period, the patients will all be supplied with AZR-MD-001 placebo. Patients will be informed that they will receive only placebo during the 2-week run-in period. Patients (or a caregiver) will apply approximately 5 mg using a dosing aid supplied by Azura Ophthalmics. Patients will use their washed index finger or an applicator (Cohort 1 only) to apply the drug to the tarsus of the lower lid of both eyes in the evening just before bedtime. The patient will then blink several times to transfer a portion of the drug from the lower eyelid to the upper eyelid.

During the Expansion Cohort qualification period, the patients will all be supplied with AZR-MD-001 placebo (“Vaseline”) at the baseline visit (single dose). During the active treatment period, patients (or a caregiver) will apply approximately 5 mg using a dosing aid supplied by Azura Ophthalmics. Patients will use their washed index finger to apply the drug to the tarsus of the lower lid of both eyes in the evening just before bedtime. The patient will then blink several times to transfer a portion of the drug from the lower eyelid to the upper eyelid.

To minimize the risk for noncompliance with the dosing instructions patients enrolled into the

clinical study will be given dosing instructions, will be observed by site personnel applying study placebo at the baseline visit, and will have access to instructional dosing videos. Only patients demonstrating compliance with the provided dosing instructions can be enrolled into the clinical study.

Following the run-in period in Cohort 1, the patient, investigator, site personnel, and the sponsor study team will be masked to the treatment assignment for the 3 month treatment period. All study medication will be provided in identical tubes and cartons to maintain masking of the study. The AZR-MD-001 vehicle was designed to have the same appearance as the active drug.

Following the qualification period in the Expansion Cohort, the patient, staff members performing all safety and efficacy assessments, site personnel (with the exception of designated personnel who are responsible for drug accountability) and the sponsor study team will be masked to the treatment assignment for the 6 month treatment period. All study medication will be provided in identical tubes and cartons to maintain masking of the study. Due to the difference in colour between the active and placebo treatments, which are in opaque tubes, designated personnel who are responsible for drug accountability will not perform any safety or efficacy assessments and will not discuss assigned treatment(s) with staff members who are performing safety or efficacy assessments.

For Cohort 1, patients will be randomized to receive AZR-MD-001 ointment/semi-solid drug (i.e., 0.1%, 0.5% or 1.0%) or AZR-MD-001 vehicle in a 4:1 treatment allocation ratio. For the Expansion Cohort, patients will be randomized to receive AZR-MD-001 ointment/semi-solid drug (i.e., 0.5% or 1.0%) or AZR-MD-001 placebo in a 1:1:1 ratio on day 0.

To obtain a screening number at the screening visit the site will access an electronic data capture (EDC) system and complete the appropriate electronic Case Report Form (eCRF). The numbers will be assigned sequentially by site.

The automated IWRS system will provide the site with the specific medication kit number(s) to use for each qualified patient at the baseline visit. At the baseline/randomization visit, patients meeting all inclusion/exclusion criteria, will be placed in one of the strata for either Cohort 1 or the Expansion Cohort. A randomization number will be assigned to each patient corresponding to the treatment arm they are assigned to. The numbers will be assigned sequentially in order of enrollment within the patient's stratum. The IWRS system will report a medication kit number to use for each patient corresponding to the randomization number.

The site will dispense the study medication kit assigned by the IWRS system. Sites will log onto the IWRS system at all subsequent study visits to obtain medication kit number for dispensing study medication. Sites will receive an IWRS confirmation notice for each transaction. All notifications are to be maintained with the study source documents.

6.4 CONCOMITANT THERAPY

Not-applicable: Patients must have discontinued and be willing to remain off all other ophthalmic preparations including artificial tears during the study.

6.4.1 RESCUE MEDICINE

In the event that rescue medication is required for worsening signs or symptoms of MGD and/or dry eye disease during the course of the study, patients will be provided an appropriate rescue regimen by the investigator/treating clinician, and may be exited from the study.

Dosing Hylo-Forte® (or an equivalent product) approximately 5 minutes before study ointment has been reported to enhance either the safety or tolerability of AZR-MD-001.

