Patients should refrain from using any ophthalmic preparations other than study treatment in order to obtain an accurate assessment of their signs and symptoms. Patients should be instructed to

communicate any changes to their ophthalmic preparations other than study treatment at their next study visit.

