8.1.2. Sensitivity Analyses of Primary Efficacy Endpoints

8.1.2.1. Last Observation Carried Forward

The primary efficacy analyses will also be performed using LOCF imputation as a sensitivity analysis. This analysis will use the ITT Set.

The change from baseline in MGYLS and OSDI total scores will be analyzed as described in [Section 8.1.1](#), based on observations using LOCF imputation as described in [Section 5.3.2](#).

8.1.2.2. Evaluation of Potentially Confounding Medications/Therapies at Month 3

The use of potentially confounding medications or therapies at Month 3 will be evaluated by tabulating the number of patients with medications that potentially affect Month 3 OSDI results, and, if a sufficient number of patients meet those criteria, repeating the OSDI analysis with a dichotomous variable indicating the presence/absence of such medications or therapies.

Potentially confounding medications or therapies will be identified as those having a Grade 4 protocol deviation with deviation class of concomitant medications/therapies. The duration of the deviation will include both the duration of medication/therapy usage and the subsequent washout period. Therefore, any such deviation whose start and stop dates overlap with the Month 3 visit date record on the Study Visits eCRF, will classify that patient as having a potentially confounding treatment for the Month 3 visit.

The number of patients with potentially confounding treatments at the Month 3 visit will be tabulated. Those patients will also be flagged in listings. If >10% of patients in the ITT Set have potentially confounding treatments at Month 3, an additional sensitivity analysis of the OSDI change from baseline will be performed. Specifically, the change from baseline in OSDI will be analyzed using an ANCOVA model similar to that described in [Section 8.1](#), with baseline MGYLS score as a covariate and treatment, duration of disease category, and baseline MGS score category as factors, with the presence of a potentially confounding treatment at Month 3 (i.e., yes or no) as an additional factor in the model. This analysis will be performed on the ITT Set, using multiple imputation.

The following pseudocode will be used:

```
PROC GENMOD data=xxx;  
  Where visit='Month 3';  
  CLASS treatment (ref = 'AZR-MD-001 PLACEBO') duration baseMGS;  
  MODEL chg =treatment base duration baseMGS confound;  
  LSMEANS treatment;  
run;
```

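### The protocol bars all other ophthalmic preparations yet reports a benefit from a pre-dose drop, and use read as permitted might escape the SAP's confounder flag for OSDI

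*Protocol*

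**What the plan says.** **The ban.** Protocol 6.4: "Patients must have discontinued and be willing to remain off all other ophthalmic preparations including artificial tears during the study". Section 5.3 repeats it and gives the reason: "Patients should refrain from using any ophthalmic preparations other than study treatment in order to obtain an accurate assessment of their signs and symptoms". Section 5.2 excludes anyone unwilling to abstain from artificial tears and ocular lubricants.

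**The statement beside it.** Section 6.4.1, headed as rescue medicine, says that a named product or an equivalent, dosed about 5 minutes before the ointment, "has been reported to enhance either the safety or tolerability of AZR-MD-001". It is not limited to Cohort 1, although the protocol marks other items that way. It does not say whether such use is allowed, counts as rescue, or is a deviation.

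**What the SAP does with confounding treatment.** Section 8.1.2.2: "Potentially confounding medications or therapies will be identified as those having a Grade 4 protocol deviation with deviation class of concomitant medications/therapies". The deviation must overlap the Month 3 visit date. Affected patients are counted, and "Those patients will also be flagged in listings". An OSDI model with a confounder term is run only if more than 10% of the ITT Set is affected, all arms together. SAP 4.3 and 7 remove a patient from the Per-Protocol set only for a Grade 4 or 5 deviation. The rules for assigning grades are in a separate deviation-definitions document.

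**Where use would otherwise show.** SAP 10.3 summarises concomitant medication by treatment, split into ophthalmic and non-ophthalmic, and flags study-eye ophthalmic medication in the listing. Medications are recorded at every visit. The SPEED form asks about lubricating drops, but that item does not enter the score in SAP 5.2.8.

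**The concern.** Sites have two messages and no rule that joins them. One site could forbid the drop and record any use as a deviation. Another could treat 6.4.1 as leave to offer it and record only a concomitant medication. The SAP's handling of confounding for OSDI runs entirely through deviation grade, so the same behaviour could be flagged at one site and not at another.

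Use could also differ by arm. The statement concerns tolerability of the active product, and in the Expansion Cohort the ointments can be told apart by eye: Protocol 6.3 restricts the staff who handle drug accountability "Due to the difference in colour between the active and placebo treatments".

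OSDI total score is a primary endpoint. In SAP 8.1.1 the 0.5% OSDI comparison is the second step of the hierarchy, and both 1.0% comparisons wait on it.

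**Working it through.** **1. The plan's own OSDI figure.** Protocol 9.1.2 gives SDs of 6.31 (control) and 8.34 (high dose), a difference of 4.52, 90% power and a two-sample t-test at 0.05 (two-sided).

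- SD = √[(6.31² + 8.34²)/2] = 7.395.
- n per group = 57 by normal approximation and 58 by the exact t-test. The stated 58 reproduces and is not in dispute.

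**2. Planned contrasts (SAP Table 1, OSDI change at Month 3).**

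- 0.5% versus placebo: 8.36 − 0.81 = 7.55.
- 1.0% versus placebo: 5.33 − 0.81 = 4.52.

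**3. Size of a possible shift.** Shift = (excess proportion of users in one arm) × (OSDI effect per user). Neither term is in the documents, so both are assumed: an excess of 10%, 20% or 30%, and an effect of 2 or 4.5 points. The 4.5 is the plan's minimally important difference, borrowed only as a reference value.

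| Excess users | Effect per user | Shift | Share of 7.55 | Share of 4.52 |
|---|---|---|---|---|
| 10% | 2 | 0.20 | 2.6% | 4.4% |
| 10% | 4.5 | 0.45 | 6.0% | 10.0% |
| 20% | 2 | 0.40 | 5.3% | 8.8% |
| 20% | 4.5 | 0.90 | 11.9% | 19.9% |
| 30% | 2 | 0.60 | 7.9% | 13.3% |
| 30% | 4.5 | 1.35 | 17.9% | 29.9% |

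The shift favours the drug if the excess is in an active arm and works against it if the excess is in placebo.

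**4. What the pooled trigger leaves out.** 10% of 225 is 22.5, so the sensitivity model needs at least 23 patients. Up to 22 graded users would be counted and listed but not modelled, however they fall across arms. With 75 per arm:

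- 11 in each active arm (11/75 = 14.7%): shift 0.29 or 0.66 points.
- All 22 in one arm (22/75 = 29.3%): shift 0.59 or 1.32 points.

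**5. Effect on one test taken alone** (SD 7.395; SE = 7.395 × √(2/75) = 1.208; normal approximation). With b the shift, the two-sided rejection rate when the drug has no effect is 1 − Φ(1.96 − b/SE) + Φ(−1.96 − b/SE).

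| Excess | Effect per user | Rejection rate, excess in active (nominal 0.05) | Power for 4.52, excess in placebo (0.963 with none) |
|---|---|---|---|
| 11/75 | 2 | 0.057 | 0.938 |
| 11/75 | 4.5 | 0.085 | 0.892 |
| 22/75 | 2 | 0.077 | 0.903 |
| 22/75 | 4.5 | 0.194 | 0.755 |

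These are illustrations for a single contrast. They are not error rates for the full hierarchy.

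**The case against.** A reader might infer that lubricant use would go unflagged and would bias OSDI in the drug's favour. The documents support neither part.

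- **Use is not invisible.** Protocol 5.3 asks patients to report changes in ophthalmic preparations at the next visit. SAP 10.3 tabulates recorded medication by arm and flags study-eye ophthalmic products. What may be missed is the confounder flag and what depends on it.
- **Grading is not left to the site alone.** SAP 7 has the investigator and an interdisciplinary team grade deviations, with a further multidisciplinary review before the database freeze. The definitions document is not available here, so it may already place pre-dose use in Grade 4. The right word is might, not would.
- **Direction is open.** Tolerability points towards excess use in the active arms. But 6.4.1 also covers rescue for worsening signs or symptoms, and rescue use could concentrate in placebo.
- **The effect per user may be small.** The use described is one drop before an ointment applied twice weekly at bedtime. Nothing in the documents supports 4.5 points, which is a threshold for meaningful change and not a lubricant effect. Quoting the shift only against 4.52 would also overstate it, because the first OSDI test is the 0.5% contrast, with 7.55 expected.
- **Adjustment is not a cure.** Use begins after randomisation and may be a consequence of treatment, so an ANCOVA term for it does not recover an unbiased treatment effect.

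All five stand, and they limit the point. They do not remove the conflict between sections, and the by-arm medication table shows use without examining its bearing on OSDI.

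**Conclusion.** The conflict is real: Protocol 5.2, 5.3 and 6.4 cannot be applied consistently alongside 6.4.1 as written. Its statistical consequence is narrow. Pre-dose lubricant use that is taken as permitted, or graded below 4, might escape the SAP 8.1.2.2 flag, the OSDI sensitivity model and the Per-Protocol exclusion, although it would still appear in the medication table and listing if recorded. Even graded use is modelled only above a threshold that pools the arms and so ignores imbalance.

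Under the assumed excess (10% to 30% in one arm) and effect (2 to 4.5 points per user), the OSDI contrast moves by 0.2 to 1.35 points in either direction. That is about 3% to 18% of the 7.55 expected for 0.5%, or 4% to 30% of the 4.52 for 1.0%. The protocol does not describe the named product; it is read here as a lubricating eye drop.

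This does not show that the OSDI result is biased. It shows that the plan could not tell readers whether it was. Because OSDI is a primary endpoint and the remedy is cheap, it should be corrected before unmasking.

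**What to change.** **Protocol.** Reconcile 5.2, 5.3, 6.4 and 6.4.1 so that sites have one rule and know how pre-dose use is to be recorded. No rule is proposed here.

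**SAP 8.1.2.2, before unmasking.**

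1. Identify any ocular lubricant use overlapping the Month 3 assessment from the concomitant medication records, regardless of deviation grade.
2. Show the count by arm next to the OSDI result.
3. Run the OSDI sensitivity analysis regardless of the pooled 10% trigger.
4. Label it supportive, and say why: lubricant use is post-randomisation.

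In the same edit, settle that model's covariate. The text of 8.1.2.2 names baseline MGYLS, while the primary OSDI model in 8.1.1 uses baseline OSDI.

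**Cost.** A protocol clarification, one flag derived from data already collected, and one further model run. Sample size, visits and the primary analysis do not change. The flag can only capture use that sites record, which is why the protocol wording has to be settled too.

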7 STUDY INTERVENTION DISCONTINUATION AND PARTICIPANT DISCONTINUATION/WITHDRAWAL

7.1 DISCONTINUATION OF STUDY INTERVENTION

Patients can voluntarily withdraw from the study at any time. The investigator and Azura Ophthalmics can withdraw a patient from the study at any time for any reason. Additionally, patients can be discontinued from the study by an investigator if any of the following criteria are met:

- patient develops (or had an exacerbation of) any medical condition that, in the opinion of the investigator, would have put the patient at an unacceptable medical risk or compromised the patient's ability to participate in the study
- patient is unwilling or unable to continue to comply with study procedures
- patient becomes pregnant

The study can be stopped at the study site(s) at any time by the site investigator(s). Azura Ophthalmics can also stop the study (and/or the study site[s]) with appropriate notification.

If a patient discontinues participation in the study early, every attempt must be made to complete the exit procedures. Notification of early patient discontinuation from the study and the reason for discontinuation should be made to your site CRA and Azura Ophthalmics, and should be clearly documented on the appropriate eCRF.

7.2 PARTICIPANT DISCONTINUATION/WITHDRAWAL FROM THE STUDY

The investigator and Azura Ophthalmics have the right to withdraw a patient from the study at any time for any reason. When possible, the decision to withdraw a patient from the study should be discussed with Azura Ophthalmics.

Patients who are withdrawn early from the study should have early exit visit procedures completed at the time of withdrawal, or at their next scheduled visit, whenever possible.

7.3 LOST TO FOLLOW-UP

A patient will be considered lost to follow-up if he or she fails to return for 2 consecutive scheduled visits and is unable to be contacted by the site staff member.

The following actions must be taken if a participant fails to return to the clinic for a required study visit:

- The site will attempt to contact the participant and reschedule the missed visit within the specified visit window (see Table 1.3) and counsel the patient on the importance of maintaining the assigned visit schedule and ascertain if the participant wishes to and/or should continue in the study.
- Before a patient is deemed lost to follow-up, the investigator or designee will make every effort to regain contact with the participant (where possible, 3 telephone calls and, if necessary, a certified letter to the patient's last known mailing address or local equivalent methods). These contact attempts should be documented in the patient's medical record or study file.
- Should the patient continue to be unreachable, he or she will be considered to have withdrawn from the study with a primary reason of lost to follow-up.

8 STUDY ASSESSMENTS AND PROCEDURES

8.1 EFFICACY ASSESSMENTS

8.1.1 COHORT 1: PRIMARY EFFICACY MEASURES

Primary efficacy measures are divided into endpoints for MGD and endpoints for evaporative dry eye (EDE). The primary efficacy measures for MGD are change from baseline to Month 3 in meibum gland secretion score (MGS) (0 to 45 scale), change from baseline to Month 3 in the number of Meibomian Glands Yielding Liquid Secretion (MGYLS) (0 to 15 scale), and the

proportion of patients improving on both a gland score (e.g., MGS or MGYLS) and a patient reported outcome measure (e.g., OSDI). A patient will be considered to be a meibum quality responder at a post-randomization visit if the MGS score in the study eye is > 12 , MGYLS score > 2 , or MGYOLS score > 2 . The primary efficacy measures for EDE are change from baseline to Month 3 in Tear Break-up Time (TBUT), change from Baseline to Month 3 in OSDI measures, change from baseline to Month 3 in eye dryness measured using a visual analogue scale (VAS), and proportion of patients with a Total OSDI change from baseline > 4.5 , the known minimally important clinical difference (MICD) for early to moderate disease, at Month 3. A patient will be considered to be an evaporative DED responder at a post-randomization visit if TBUT > 10 seconds, a Schirmer's test ≥ 10 mm, a Total OSDI < 13 , or a SPEED Score < 6 , or an Average VAS or Worst VAS score decreased by ≥ 5 is observed.

8.1.2 COHORT 1: SECONDARY EFFICACY MEASURES

Secondary efficacy measures include the meibum gland secretion score (MGS), the number of Meibomian Glands Yielding Liquid Secretion (MGYLS), TBUT, OSDI measures, visual analogue scale (VAS), Schirmer's test without anesthesia, conjunctival redness score, sodium fluorescein corneal staining (Oxford scale), and lissamine green conjunctival staining. Refer to Section 1 for a complete list and specific timings of additional efficacy measures.

8.1.3 COHORT 1: DATA REVIEW COMMITTEE (DRC)

Safety oversight will be under the direction of a DRC composed of individuals with the appropriate expertise (see Section 4.3). Members of the DRC should be independent from the study conduct and free of conflict of interest, or measures should be in place to minimize perceived conflict of interest. The DRC should meet at least monthly to assess safety and efficacy data on each arm of the study. The data of the first Cohort will be reviewed by the DRC prior to proceeding to the next dose level. The DRC will operate under the rules of an approved charter that will be written and reviewed at the organizational meeting of the DRC. At this time, each data element that the DRC needs to assess will be clearly defined. The DRC will provide its input to Azura Ophthalmics, the IEC and regulatory authorities as necessary.

Interim safety and preliminary efficacy evaluations will be performed and reviewed by the DRC when the first 10 patients in Cohort 1, Group 3 completes the Month 3 visit (First Interim Analysis) and when the last patient enrolled in Cohort 1, Group 4 completes the Month 3 visit (Second Interim Analysis). There is no plan to stop the study for efficacy on the basis of the interim analyses. However, termination due to futility may occur. Statistical significance will be declared at the time of the interim analysis.

